### 3.1 Inclusion Criteria

### PATIENTS MUST BE $\geq$ 18 AND $\leq$ 65 YEARS AND HAVE TWO POSITIVE SEROLOGICAL TESTS FOR CHAGAS DISEASE (INDIRECT IMMUNOFLUORESCENCE, INDIRECT HEMMAGLUTINATION, OR ELISA) and

ANY ONE OR MORE of the following markers of cardiac involvement:

### a. Abnormal 12 lead ECG: at least two of the following:

- i. Complete right bundle branch block
- ii. Complete left bundle branch block
- iii. Left anterior fascicular block
- iv. Left posterior fascicular block
- v. Ventricular premature beat
- vi. First degree AV block > 220 ms, in the absence of drugs that slow AV conduction
- vii. Mobitz type I AV block, in the absence of drugs that slow AV
- viii. Sinus bradycardia < 50 bpm or sinus pauses > 3.0s, in the absence of sinus node blocking drugs
- ix. Primary ST-T changes
- x. Abnormal Q waves
- xi. Low voltage of QRS
- xii. Atrial fibrillation

### OR

- Abnormal 12 lead ECG: one of the following
  - 1) Mobitz type II, advanced or third degree AV block

### OR

**b.** increased cardio thoracic ratio > 0.50 at baseline on upright chest X ray

- OR
- **c.** Evidence of regional wall motion abnormality (hypokinesis, akinesis or dyskinesis) or reduced global left ventricular systolic function LVEF < 50% (2D-Echo, RNA, LV ventriculography) or incressed left ventricular dyastolic diameter (> 55 mm) on 2D-Echo

### OR

**d.** complex ventricular arrhythmias (multiform > 10/hour, couplets or NSVT) on 24 hour ambulatory ECG monitoring

### 3.2 Exclusion Criteria

- a) NYHA heart failure class IV or decompensated heart failure
- b) Evidence of concomitant CAD or other etiology of dilated cardiomyopathy.
- c) Previous treatment with antitrypanosomal agents or an accepted indication for antiparasitic therapy (e.g. reactivation of Chagas infection due to immunosuppression by several diseases or treatment with steroids)
- d) Inability to comply with follow-up
- e) History of severe alcohol abuse within 2 years
- f) Known chronic renal insufficiency (serum creatinine > 2.5 mg/dl or 200μmol) or hepatic insufficiency (AST/ALT > 3x normal)
- g) Pregnancy or breast feeding
- h) Megaesophagus with swallowing impairment
- i) History of severe alcohol abuse within 2 years
- j) Other severe disease significantly curtailing life expectancy

Patients living in inadequate housing conditions that may predispose to *t. cruzi* re-infection will not be excluded; instead this condition will be appropriately documented and further analysis will be performed.

#### 4. STUDY DESIGN AND TREATMENTS

#### 4.1 Sample Size Calculation

The sample size calculation for this trial is based on observational data indicating that the five year rate for the time to event of the composite endpoint of death, resuscitated cardiac arrest, development of new heart failure, life threatening non-fatal arrhythmias, thromboembolic phenomena, and need for pacemaker implantation or ICD in the placebo group will be around 30%. Event rate calculations were based on pooled data from longitudinal population studies in patients with  $CD^{35, 36}$ . These studies indicate a 5% annual mortality with sudden cardiac death being responsible for 60% of the mortality. However, event rates among patienta entered into trials is generally lower so we have assumed a 3% -4% annual mortality. It is expected that the annual morbidity rates will also be similar givingh a composite event rate of 6%-8%/yr.

In order to have 90% power at the 5% significance level (two sided) with an overall drop-out rate of 20%, to detect a 20% risk reduction the trial will require the enrolment of at least 3000 patients. Analysis of the primary and secondary outcomes will be performed according to the intention-to-treat principle.

A sensitivity analysis wil be performed in patients with prior sustained ventricular tachycardia, thromboembolic phenomena or heart failure hospitalization. This analysis will allow that the mentioned events are not included as a primary outcome. Also, in patients with advanced AV block at onset, pacemaker insertion will not be counted as an endpoint.

#### 4.2 Treatment

#### 4.2.1 Study Drug

Study drug supply will be coordinated by the Brazilian Coordinating Center with support by the PHRI-BENEFIT Project Office. Benznidazole 100 mg tablets and matching benznidazoleplacebo tablets will be supplied. Non-study medications such as ACE inhibitors, diuretics, digoxin, beta-blockers, amiodarone, ASA or warfarin, will not be supplied. Patients will be encouraged to remain adherent to concomitant therapy according to current guidelines.

#### 4.2.2 Randomization

Patients recruited following strict inclusion and exclusion criteria will be randomized double-blindly to receive 300mg/day of benznidazole in two daily doses for 40 to 80 days or matching placebo using the same administration daily scheme.

As seen on the Table for the Therapeutic Dosage, in page 5, both groups will be treated for 40 to 80 days, according to a direct relationship with the patient's weight: thus, a patient weighing 40kg will be treated with 300mg daily for 41 days, weighing 51kg, for 51 days, 65kg = 65 days and so on, up to the maximum of 80kg, when a patient with this last weight will receive 300mg daily for 80 days. Hence, the maximum dose to be received, even for patients weighing more than 80 kg will be, at the end o the treatment period, 24g

Patients will be followed with attention paid to development of side effects including dermatitis, leucopenia, peripheral neuropathy and gastrointestinal symptoms. Potential toxic effects will be scrutinized with clinical and laboratory evaluation, including white cell count and hepatic function tests (AST, ALT, serum creatinine). These evaluations will be conducted at baseline, three weeks and 40 to 90 days after the beginning of treatment.

- Additional data will be collected in subgroups of patients to investigate other hypotheses:

#### 4.2.3 Method of assigning patients to treatment group

The patient identification (ID) and treatment numbers will be provided at randomization by a centralized randomization service located at the Brazilian Coordinating Center. A system similar to that used in the CREATE and HOPE trials conducted by the PHRI will be designed. Alterbatively if all sites have access to a computer with internet access, local randomization may be performed in a secure way. Randomization will be 1:1 with stratification according to centre using a random block size. Subsequent treatment numbers for study drug re-supply will be provided.

#### 4.2.4 Permitted concomitant therapy

Any concomitant therapy, including treatments demonstrated to be effective in the study population is permitted.

#### 4.2.5 Treatment adherence

Study continuation is recommended unless clear contraindications arise, study drug should be continued or only briefly interrupted ( $\leq$  less than 1 week). The only clear criteria for permanent discontinuation of benznidazole study medication are: (i) significant leukopenia (< 2,500), (ii) serious gastrointestinal symptoms (iii) severe allergic dermopathy, and (iv) peripheral sensitive neuropathy. In other situations, discontinuation of study drug will be discouraged as much as possible. Symptomatic treatment for mild symptoms (nauseas, vomiting, allergy) is allowed. Study drug accountability, as well as all pre-specified concomitant medications, must be appropriately recorded at each scheduled visit.

#### 5. OUTCOMES

#### 5.1 Primary Outcome

The first occurrence of any of the following clinically significant outcomes:

- 1. Death
- 2. Cardiac arrest, requiring defibrillator or cardioversion
- 3. Documented sustained ventricular tachycardia requiring cardioversion
- 4. New development of symptomatic congestive heart failure fulfilling at least two of the following: a) signs and symptoms of CHF, b) Chest X-ray findings compatible with CHF, c) need for intravenous therapy, and d) hospital admission due to CHF
- 5. Pacemaker or implantable cardiac defibrillator indication.
- 6. Stroke or any other thromboembolic event in patients with no prior thromboembolic phenomena
- 7. Heart transplant

#### 5.2 Secondary Outcomes

a) Response to therapy based on baseline PCR (+/-) and response at 24 month and end of follow-up

- b) New development of any of the following echo changes; segmental wall motion abnormalities, ventricular aneurysm, reduction in LV ejection fraction > 5%, increase in LVDD > 5.0 mm compared with baseline.
- c) New 12 lead ECG alterations (complete bundle branch block, fascicular block, advanced atrio-ventricular block, atrial fibrillation, etc).
- d) Progression of NYHA functional class by at least one category.

#### 6. FOLLOW-UP

#### 6.1 Follow-up Schedule

The clinical and laboratory follow-up will aim primarily in evaluating treatment safety and detection of side effects. For this purpose the first follow-up visit will be scheduled  $11\pm 2$  days after the beginning of treatment, when allergic deramtitis typically occurs. The second follow-up visit will be scheduled 3 weeks  $\pm 3$  days after the beginning of treatment aiming at the detection of leucopenia, and a final visit will always be scheduled at the end of the treatment period (40 to 80 days, with tolerance of +10 days). Additional visits will occur 6 months after the end of treatment, and from then on annually until the end of the study.

#### 7. STUDY ORGANIZATION

The PHRI-BENEFIT project office at McMaster University in Hamilton, Canada will coordinate the study. BENEFIT is a collaborative effort between the PHRI, and several Central and South America and investigators interested in Chagas disease from Argentina, Brazil, Colombia, and Venezuela, and will also aggregate Peru and Bolivia, El Salvador. It is expected that 75 centers are necessary to enroll 3000 patients (at least 40 patients per centre).

National coordinators will be responsible for recruitment and implementation of the trial. National coordinators will select the study sites and principal investigators in each country. It is estimated that Argentina and Brazil will enroll 2000 patients (1000 each) and 25 centres are needed in each country. Colombia and Venezuela will enroll another 1000 patients (500 each) with another 25 centres between the two countries. To enroll 3000 patients in 24 months we will need to recruit 125 patients monthly. This will be approximately 2 patients per month per center. These estimates suggest that the enrolment phase for BENEFIT is feasible. Drug distribution and labeling will be coordinated from the Brazilian Coordinating Centre.

#### 7.1 BENEFIT Operations Committee

The Operations Committee will consist of a select group of Steering Committee members chosen for their specific expertise, time availability and experience. This group will be responsible for ensuring that study execution and management are of the highest quality. The Operations Committee will convene regularly by teleconference and/or face-to-face meeting (at least every 2 months) to discuss and report on the ongoing supervision of the study.

#### 7.2 Steering Committee

The Steering Committee is composed of a group of national coordinators who will mostly be cardiologists, since patients with CD are most often cared for by cardiologists. This group will be supplemented with experts in CD, and electrophysiology. The committee has the overall responsibility for producing and conducting a scientifically sound design and ensuring accurate reporting of the study. In that capacity, the Steering Committee must address and resolve scientific issues encountered during the study. This committee will meet at least twice a year.

All proposed ancillary research investigations on patients enrolled in BENEFIT must be approved by the Steering Committee. The primary scientific publication reporting the study results is the responsibility of the Steering Committee. Collaborating Investigators or members of the various study committees wishing to prepare secondary publications must submit proposals and manuscripts to the Steering Committee for approval. However, the final decision on the contents of all publications will be the responsibility of the BENEFIT Operations Committee.

#### 7.3. Data Safety Monitoring Board

The Data Safety Monitoring Committee Board (DSMB) will include an epidemiologist, 2 prominent cardiologists, as well as a statistician. The DSMB provide on-going review of the safety of all the investigational treatments. To facilitate its responsibilities, the DSMB will have an Associated Statistician who will receive study data directly from the Central Study Database and who will remain independent of the trial management team.

The DSMB Associated Statistician, being unblinded, will not be able to edit/alter any part of the Central Study Database. Routine access to the treatment code will be restricted to the Chairman of the DSMB, except for emergency unblinding on a case-by-case basis.

#### **DSMB Responsibilities**

#### **Primary:**

1) Regular review of safety data and serious adverse events

2) Formal interim analyses of efficacy data

3) Feedback to the Operations Committee

#### Secondary:

1) Respond to special requests from regulatory authorities or IRBs

2) Recommendations for protocol amendments

3) Verification of the final analysis of the study will be done by the DSMB Associated Statistician

#### Safety Review

Recommendation to stop a trial early for safety reasons is, by definition, a qualitative judgement. The DSMB is composed of eminent clinicians and methodologists who are experienced with clinical trials and can be relied upon to exercise good judgment in weighing the potential risks and benefits to patients as data accumulate in this trial.

Safety aspects, and more specifically severe dermatitis and/or neuropathy will be monitored. No formal boundaries will be proposed for safety, but clear, consistent, and persistent evidence of net harm that overwhelms any benefit should be apparent. A recommendation to stop the trial will be based on the pattern of treatment effect across all endpoints, as well as the benefit/risk ratio. Two interim analyses to assess futility are scheduled at approximately 1/2 and 3/4 of the total of anticipated events.

The trial may be stopped for efficacy if a reduction in events by four standard deviations, or a three standard deviation excess occur in the first half of the trial, or if a reduction in events by three standard deviations or a 2-standard deviation excess is detected in the second half of the trial. If the upper limit of the 95% CI for the conditional power for the primary outcome falls below 15%, then, all other things being equal, the DSMB may recommend early termination.

#### 7.4. Adjudication Committee

This committee, composed of experts in the relevant fields will review, in a blinded manner; all reported outcome events to provide consistency and validity in the assessment of outcomes. Their decisions will be based on blind clinical data and they will consider the impressions of the clinical investigator. Their decisions will be used for the final analysis.

### **8. PROJECTED TEMPORAL SCHEDULE FOR THE PROJECT DEVELOPMENT**

2002 until November 2003: development and finalization of the research protocol

November 2003 to November 2004: center selection and preparation

November 2004 to February 2010: recruitment

November 2004 to February 2013: clinical follow-up

March 2013 to February 2014: results analysis and publication

## 10. APPENDIX – TABLE for number of days of treatment to the patient's body weight

Weight (Kg)	Treatment Duration (days)	
40	40	
41	41	
42	42	
43	43	
44	44	
45	45	
46	46	
47 47	47	
48 40	48 49	
49 50	49 50	
50 51	50	
51 52	51 52	
52	53 53	
55 54	54	
55	55	
56	56	
57	57	
58	58	
59	59	
60	60	
61	61	
62	62	
63	63	
64	64	
65	65	
66	66	
67	67	
68	68	
69	69 70	
70 71	70 71	
72	71 72	
72	72 73	
73 74	74 74	
75	75	
76	76	
77	77	
78	78	
79	79	
>80	80	
• Fixed 30	Fixed 300mg daily dose for all patients	

 
1 pill qam and 2 pills qpm (q12 hrs)
 
		
	
 
Each BZ pill = 100 mg (unscored)
 
	

## BENEFIT HISTORY OF PROTOCOL AND AMENDMENTS

Protocol	Date	Reason for Amendment
Original Protocol	May 12, 2003	n/a
Amendment #1	June 27, 2005	Pilot Study
Amendment #2	August 29, 2005	Pilot Study: Consent Form modification
Amendment #3	May 30, 2006	
 
Extended upper limit of age inclusion criterion from ≤65 years to ≤75 Years.
 
To revert to original version of the consent form (i.e., without amendment 2 alterations).
 

Amendment #4	Feb 02, 2009	Change of Study Medication presentation and adminsitration schedule. From scored to non-scored tablet. Heart transplant added to primary outcome composite.

10. SUBGROUP ANALYSIS
11. SENSITIVITY ANALYSIS
12. ADHERENCE TO THE PROTOCOL
13. APPROVAL

## **1. LIST OF ABBREVIATIONS**

Abbreviation	Full Word
AE	Adverse Event
AF	Atrial Fibrillation
BENEFIT	Benznidazole Evaluation for Interrupting American Trypanosomiasis
BNZ	Benznidazole
ссс	Chronic Chagas' Cardiomyopathy
CD	Chagas Disease
CI	Confidence Interval
CNS	Central Nervous System
CRT-D	Cardiac Resynchronization Therapy Defibrillator
ECG	Electrocardiogram
GEE	Generalized Estimating Equation
HR	Hazard Ratio
ICD	Implantable Cardioverter Defibrillator
ТТТ	Intention-To-Treat
IV	Intravenous
LVEDD	LV end-diastolic diameter
LVEF	Left Ventricular Ejection Fraction
MedDRA	Medical Dictionary for Regulatory Activities
OR	Odds Ratio
PCR	Polymerase Chain Reaction

PHRI	Population Health Research Institute
SAE	Serious Adverse Event
SAP	Statistical Analysis Plan
SD	Standard Deviation
VT	Ventricular Tachycardia

## **2. INTRODUCTION**

This statistical analysis plan (SAP) provides a comprehensive and detailed description of the statistical methods to be used to realize the analysis of the "Benznidazole Evaluation for Interrupting American Trypanosomiasis (BENEFIT) Trial" described in the clinical study proto col (dated February 2, 2009). The objective of a Statistical Analysis Plan is to ensure the maximum credibility of all study findings by means of a pre-specified data analysis. This plan may be revised during the study to accommodate protocol amendments and/or to make changes to adapt to unexpected issues in study execution and/or data that affect planned analyses. All changes will be made by individuals who are blinded to the outcomes by treatment group. The SAP is a working document that will be amended as the trial progresses. The final version of the SAP will be signed off prior to database lock

The BENEFIT trial is a multicenter, prospective, randomized, double-blind, placebo-controlled clinical trial of 2,855 patients with chronic Chagas' cardiomyopathy(CCC) in Latin America. The role of persistent low grade *T. cruzi* infection in the progression of CCC remains a matter of discussion and the efficacy and safety of Benznidazole in this setting has not been tested in a large-scale multicentre clinical trial. Similarly outcome measures to determine efficacy of treatment are limited by the long time serologic Chagas markers take to become negative.

In BENEFIT, Chagasic patients aged  $\geq 18$  years and  $\leq 75$  years, are eligible if, in addition to having any combination of at least 2 positive serologic tests for CD (indirect immunofluorescence, indirect hemagglutination, or ELISA), have evidence of cardiomyopathy based on the criteria outlined in Table I. Consenting patients who fulfill the eligibility criteria are randomized to receive benznidazole(BNZ) (5 mg/kg per day) or matched placebo for 60 days (randomized from November 2004 to December 2008 with 1543 patients ) or a maximum daily dose of 300mg for 60 days if weight was 60kg,, 70 days if weight was 70kg, and so on, to a maximum of 80 days(randomized from January 2009 to October 2011 with 1312 patients). (The reason for this was related with drug supply). The primary outcome is the composite of death; resuscitated cardiac arrest; sustained ventricular tachycardia(VT); new insertion of pacemaker or cardiac defibrillator; cardiac transplantation; and development of new heart failure, stroke, or systemic or pulmonary thromboembolic events. The average follow-up time will be 5.5 years, the sample size is 2753 patients pts with and the trial has a 90% power to detect a 26.5% relative risk reduction, assuming a yearly event rate of 8% in the control group of the composite primary outcome.

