### **3. PARTICIPANT ELEGIBILITY**

This is a prospective, multicenter, international double blind randomized study evaluating benznidazole versus placebo. Subjects with serological and clinical evidence of cardiac CD will be recruited to determine if benznidazole prevents mortality and progression of CCM.

Participants will be randomly allocated to treatment with 300mg/day of benznidazole or matching placebo, divided in two daily doses, for 40 to 80 days. Enrollment will begin in the end of 2004 and should be complete by February of 2009. All patients will be followed by a minimum of 4 years.

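### The SAP's power statement (90% power for a 26.5% reduction) cannot be reproduced from the inputs it states, and its sample size conflicts with the rest of the SAP

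*Supplement*

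**What the plan says.** SAP Section 2 (Introduction) gives the only power statement in the SAP: "the sample size is 2753 patients pts with and the trial has a 90% power to detect a 26.5% relative risk reduction". The control arm is taken to have events at 8% per year, and mean follow-up is put at 5.5 years. No event count, drop-out rate, non-compliance rate or formula is given.

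The same section describes a "clinical trial of 2,855 patients", and its two recruitment periods (1543 and 1312 patients) add to 2,855.

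SAP Section 3.1 sets a two-sided 0.05 level. Section 8.2.1 specifies a log-rank test with a Cox hazard ratio (HR). Section 4.1 makes the primary analysis ITT. Section 10 (Subgroup Analysis) adds that a benznidazole patient who stops complying is assumed to take on the placebo risk, but gives no rate and no link to the power statement.

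Section 4.1 of the current protocol states that, with 90% power and 20% drop-out, "to detect a 20% risk reduction the trial will require the enrolment of at least 3000 patients". It assumes about 30% of controls with an event at five years and a composite rate of 6-8% per year.

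**The concern.** The power sentence puts sample size, event rate, follow-up, power and effect side by side, so a reader can check it, and the check fails by a wide margin. The comparison with the protocol also looks odd. The SAP has 2,753 patients rather than 3,000, takes the upper end of the protocol's 6-8% rate and extends follow-up from 5 to 5.5 years, yet its detectable effect grows from 20% to 26.5%.

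At stake is how the trial's sensitivity is described. A reader who takes 26.5% at face value will think the trial was built to find only a larger effect than its stated inputs imply. If the 8% rate is what is wrong, the sentence misleads in the other direction. The reader also cannot tell whether 26.5% is the effect the ITT analysis would see or the effect in fully adherent patients.

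**Working it through.** **Inputs.** N = 2,753; control rate 8%/yr; 5.5 years; HR = 1 - 0.265 = 0.735 (SAP Section 2). Two-sided alpha 0.05 (SAP Section 3.1). Allocation 1:1 (protocol Section 4.2.3). Drop-out 20% (protocol Section 4.1 only). Assumptions: exponential event times, and every patient followed for the mean time.

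**Events needed for 90% power (Schoenfeld).**
d = 4 × (1.96 + 1.2816)² / (ln 0.735)² = 42.03 / 0.0948 = about 443.

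**Events expected from the stated inputs.**
- Control risk: 1 - exp(-0.08 × 5.5) = 0.356
- Treated risk: 1 - exp(-0.08 × 0.735 × 5.5) = 0.276
- Events: 2,753/2 × (0.356 + 0.276) = about 870

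**Power.** Φ(|ln 0.735| × √870 / 2 - 1.96) = Φ(4.54 - 1.96) = Φ(2.58) = 0.995, not 0.90. The 443 events would come from about 443 / 0.316 = 1,400 patients, where 0.316 is the average of the two risks. Solving instead for the reduction detectable with 90% power gives 19.4%.

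**Attempts to recover the stated 90%.** N = 2,753 throughout. Where there is dilution, the HR is 1 - 0.265 × adherence. The last column is the full-adherence reduction detectable with 90% power.

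| Variant | Power for 26.5% | Reduction at 90% power |
|---|---|---|
| As stated, hazard 0.08 | 99.5% | 19.4% |
| 8% read as annual risk, hazard -ln 0.92 | 99.6% | 19.1% |
| 20% loss (N × 0.8) | 98.2-98.5% | 21.2-21.6% |
| 20% loss as a constant loss hazard | 99.1-99.2% | 20.1-20.4% |
| 20% dilution, no loss | 94.5-95.2% | 23.9-24.3% |
| 20% loss (N × 0.8) and 20% dilution | 89.0-89.9% | 26.5-26.9% |
| About 27% dilution, no loss | 89.7-90.7% | 26.2-26.6% |

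Ranges cover the two readings of 8%. Freedman's formula agrees with Schoenfeld's to within about 0.3 of a percentage point. A two-proportion test, a one-sided test and N = 2,855 without dilution all stay well above 90%.

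**What 26.5% means in the rows that fit.** With 20% dilution the ITT reduction is 0.265 × 0.80 = 21.2%. With 27% dilution it is 0.265 × 0.73 = 19.3%.

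**With N = 2,855 at 8%/yr.** With no loss, 902.6 events are expected at HR 0.735, and the 90%-power reduction is 19.1%. With 20% loss it is 21.2%.

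**The protocol's figure.** For 30% against 24%: 2 × (1.96 + 1.2816)² × (0.30 × 0.70 + 0.24 × 0.76) / 0.06² = about 2,291 patients. Dividing by 0.8 gives about 2,863, so 3,000 is coherent.

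**The case against.** The strongest reply is that 99.5% and 19% treat unstated allowances as zero, when the documents assume neither complete follow-up nor full adherence. The protocol carries 20% drop-out, and SAP Section 10 has wording typical of an effect-dilution calculation. With hazard -ln 0.92, 20% loss and 20% dilution, the detectable reduction is 26.5%, matching the SAP. This stands as a plausible explanation: the fault may be missing assumptions rather than a wrong number. It is not proof. No rate accompanies the Section 10 sentence, the protocol's single 20% would be used twice, and about 27% dilution alone fits about as well.

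It is also fair that the sentence is descriptive. It alters no endpoint, test, population or alpha, and a neutral result will be judged mainly from the hazard ratio and its confidence interval.

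Three stronger readings are tempting, and the documents do not support them.
- A reader might infer that the trial's real power for 26.5% is 99.5%. That holds only with no loss, full adherence and a true 8% rate.
- A reader might infer that the event rate must really be about 3.7%/yr, where 2,753 patients give 90% power for 26.5%. That also requires no loss and no dilution. The 8% itself lies within the protocol's 6-8%.
- A reader might infer that 5.5 years is impossible, because protocol Section 8 lists "November 2004 to February 2013: clinical follow-up" while the SAP reports randomisation to October 2011. That entry is a projection which also had recruitment ending in February 2010. The SAP states no such close, and its Section 8.1.1 plans visits to year 9.

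**Conclusion.** The point holds as a failure of reproducibility. From its stated inputs, the SAP's sentence should read about 99.5% power for 26.5%, or 90% power for about 19%. With the protocol's drop-out taken as loss, it should read about 98%, or about 21-22%. Only additional, unstated allowances bring back 90% for 26.5%. In that case 26.5% is not the effect that the ITT analysis is powered for, which would be about 19-21%.

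Separately, "the sample size is 2753 patients pts" conflicts with the SAP's own 2,855, a gap of 102 patients with no explanation. The move from the protocol's 20% to 26.5% is also unexplained.

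The figures rest on exponential event times, a common follow-up of 5.5 years and a constant hazard ratio. The conclusion does not depend on how 8% is read or on the choice between the Schoenfeld and Freedman formulas. Severity: should-fix. The stated precision is unreliable, but the planned analysis is unchanged.

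**What to change.** Rewrite the sentence in SAP Section 2 before database lock, by staff blinded to outcomes by treatment group, as that section already allows.

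1. Use one N, the 2,855 randomised, or explain what 2,753 counts.
2. Give the expected number of events and the loss and non-compliance allowances used.
3. Then either restate the ITT effect detectable with 90% power under those inputs (at 8%/yr, about 19% with no loss and about 21% with 20% loss), or label 26.5% as a full-adherence effect and give the corresponding ITT effect.
4. Say how the result relates to the protocol's 20%.

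While editing, note how protocol Section 3's statement that "All patients will be followed by a minimum of 4 years" fits with randomisation to October 2011 and a 5.5-year mean.

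The cost is a short recalculation and a few lines of text. No patients, visits or analyses change.
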